### 5.2 Study drug (LDE225)

#### 5.2.1 Packaging and labeling

LDE225 capsules will be supplied by Novartis as 200-mg hard gelatin capsules for oral use, packaged in bottles, and will be administered on a flat scale of 800 mg/day for all patients.

Medication will be labeled for Clinical Trial use and will include storage conditions for the drug and the medication number but no information about the patient.

Table	Packaging and labeling	
Study drugs	Packaging	Labeling (and dosing frequency)
LDE225	Capsules in bottles (200 mg)	Labeled as "LDE225"

### **5.2.2 Supply, receipt and storage**

Study drug must be received by a designated person at the study site (usually the site pharmacist), handled and stored safely and properly, and kept in a secured location to which only the investigator and designated assistants have access. Upon receipt, LDE225 should be stored according to the instructions specified on the drug labels. Study medication will be dispensed by an authorized person at the investigator's site (usually the pharmacist).

Patients will be provided with adequate supply of LDE225 for self-administration at home until at least their next scheduled study visit (*i.e.* at least a 4-week period). Patients should be instructed to store LDE225 capsules in the refrigerator.

### **5.2.3 Drug compliance and accountability**

#### **5.2.3.1 Drug accountability**

Clinical drug supply must be accounted for and patients will be asked to return all unused study drug and packaging on a regular basis, at the end of the study or at the time of study drug discontinuation.

At the conclusion of the study, and, as appropriate during the course of the study, the Investigator will return all used and unused study drug, packaging, drug labels, and a copy of the completed drug accountability ledger to Novartis.

### **5.2.4 Disposal and destruction**

The drug supply will be destroyed at a Novartis facility, Drug Supply group or third party, as appropriate. Study drug destruction at the Investigational Site will only be permitted if authorized by Novartis in a prior agreement and if permitted by local regulations.

## 6 Schedule and Assessments

### 6.1 Study flow and visit schedule

	Screening Evaluation	Repeat Biopsy a	Day 1	Day 14	Prostatectomy, Day 28 ( $\pm 3$ )	Follow-up, 1 mo Post-Op	Follow-up, 2 mo Post-Op	Follow-up, 3 mo Post-Op j
Informed consent	X							
Medical history	X			X	X			
Medication review	X			X	X			
Physical exam	X			X	X			X
Vital signs	X			X	X			X
Height and weight	X			X	X			
Performance status	X			X	X			X
ECG	X			X	X			
CT and bone scan b	X							
Heme labs, Coags c	X			X	X			X
Chemistries, incl. CK d	X			X	X			X
PSA (standard) e	X				X			X
PSA (ultrasensitive) e						X	X	
Plasma for PKs f	X				X			
LDE225 dose g (Arm 1)				X-----X				
Observation g (Arm 2)				X-----X				
Toxicity assessment				X-----X				
Prostatectomy specimen h					X			
Pathologic review i	X	X			X			

a: A repeat 12-core (pre-treatment) prostate biopsy should be conducted within 4 weeks ( $\pm 4$  days) of starting protocol therapy. Tissue will be subject to mRNA analysis.  
b: Staging CT (if allergic to CT scan contrast, obtain MRI with contrast); CT and Bone scan must be performed within 2 months of starting protocol therapy  
c: Hematology laboratories include hemoglobin, hematocrit, white blood cell count with differential, and platelets. In addition, PT/INR and APTT should be collected.  
d: Chemistry laboratories include sodium, potassium, chloride, bicarbonate, urea nitrogen, creatinine, glucose, calcium, albumin, total protein, bilirubin, alanine aminotransferase (ALT), aspartate aminotransferase (AST), and alkaline phosphatase. In addition, creatine kinase (CK) should be measured at baseline, and then only for patients receiving LDE225.. Samples drawn for CK levels will be taken from both arms.  
e: Serum PSA should be obtained pre-treatment and on the day of surgery, and at 1, 2 and 3 months post operatively. Ultrasensitive PSA testing should be run at the 1 and 2 month post-op time points.  
f: Blood samples will be collected at baseline and on the day of prostatectomy for measurement of plasma LDE225 levels.  
g: LDE225 800 mg by mouth once daily (for 4 weeks,  $\pm 3$  days) OR observation. Patients randomized to the observation arm are not required to have the C1D14 visit.  
h: Radical prostatectomy specimens to be processed at Johns Hopkins according to standard procedures, with additional 250-mg biopsies of prostate tissue frozen for analysis of mRNA expression and tissue LDE225 levels.  
i: Pathological review of outside biopsy slides at the Johns Hopkins Hospital are required to confirm Gleason grade of disease at screening. Pathologic evaluation will also occur with frozen tissue from repeat biopsies and with tissue from radical prostatectomy.  
j: The post-operative evaluation at 1 and 2 months after prostatectomy may take place over the telephone or in person, but patients are required to have labs collected as indicated above. The 3-month follow-up should involve an office visit. After the 3-month visit, PSA will continue to be collected according to the treating physician's standard practice (usually once every 3 months).

### **6.1.1 Screening Evaluation**

The screening examination must start with the Informed Consent procedure. The investigator is obliged to give the patient thorough information about the study and the study related assessments, and the patient should be given ample time to consider his or her participation. The investigator must not start any study related procedure before ICF is signed and dated by both patient (and impartial witness, if applicable) and investigator.

## **6.2 Assessments**

### **6.2.1 Efficacy assessments**

The primary measures of efficacy in this trial are pharmacodynamic measured by the change in *Gli1* expression by qRT-PCR. In addition, efficacy will also be evaluated in secondary endpoints which will compare tumor stage, grade, surgical margin rates and tumor proliferation / apoptosis between treatment and observation arms. The proportion of patients with undetectable PSAs at three months will also be assessed in the two groups.

### **6.2.2 Safety assessments**

Safety assessments will consist of monitoring and recording all adverse events (AEs), including serious adverse events, the monitoring of hematology, blood chemistry, ECG and the regular monitoring of vital signs, and physical condition as shown in [corresponding tables](#). All patients will receive CK level monitoring at baseline, day 14 and day 28 with additional levels drawn in patients report symptoms of rhabdomyolysis during the study. For details on AE collection and reporting, refer to [the Safety section in the protocol](#).

In addition, we will pay particular attention to peri-operative adverse events (intraoperative bleeding, increased operative time, increased hospital length of stay, increased postoperative infections, wound breakdowns, etc.). These will be monitored by review of in hospital records and post-operative clinic notes.

### **6.2.3 Pharmacokinetics**

Plasma LDE225 trough levels (PK) will be measured at baseline and on the day of prostatectomy using LC-MS/MS.

### **6.2.4 Biomarkers**

For analysis of *Gli1* expression, RNA will be purified using the RNeasy Minikit (Qiagen) and then cDNA will be synthesized according to standard procedures. Quantitative PCR will then be performed using the Taqman system with primers for *Gli1* and the reference gene *HPRT1*. Applied Biosystems software will be used to calculate threshold cycle values (and thus relative expression levels). Normalized changes in *Gli1* expression between each patient pre- and post-operatively and between each group (observation versus treatment arm) will be made with 2-sided pairwise comparisons considering  $P < 0.05$  to be statistically significant.

Genome-wide mRNA expression data will also be collected with comparisons made both within and between treatment groups. This analysis will look for expression based indications of molecular pathway alterations upon exposure to LDE225 and will do so in an unbiased

way. For each array, data will be processed for statistical analysis using packages from R/Bioconductor with a mixed-effects model used to fit for each gene and to estimate expression differences between groups and an empirical Bayesian approach used to moderate log2 fold change standard errors. Functional themes will be obtained from Gene Ontology, Kyoto Encyclopedia of Genes and Genomes, the Human Protein Reference Databases and Molecular Signature Databases and used to perform enrichment analysis using Wilcoxon tests. Multiple testing corrections will be performed using the Benjamini-Hochberg method.

## **7 Safety Monitoring and Reporting**

### **7.1 Adverse Events**

#### **7.1.1 Definitions and reporting**

Information about all adverse events, whether volunteered by the subject, discovered by investigator questioning, or detected through physical examination, laboratory test or other means, will be collected and recorded and followed as appropriate. An adverse event is any undesirable sign, symptom or medical condition occurring after starting study drug (or therapy) even if the event is not considered to be related to study drug (or therapy). Study drug (or therapy) includes the drug (or therapy) under evaluation, and any reference or placebo drug (or therapy) given during any phase of the trial.

- if it is unclear what study treatment includes, list all drug(s), other therapies, changes to existing therapy, diagnostic procedure, etc. that are specified by the protocol

Medical conditions/diseases present before starting study treatment are only considered adverse events if they worsen after starting study treatment (any procedures specified in the protocol). Adverse events occurring before starting study treatment but after signing the informed consent form are recorded. Abnormal laboratory values or test results constitute AEs only if they induce clinical signs or symptoms or require therapy, and are recorded.

Information about all serious adverse events will be collected and recorded on the FDA MedWatch 3500a Form. To ensure patient safety each serious adverse event must also be reported to Novartis within 24 hours of learning of its occurrence. A serious adverse event is an undesirable sign, symptom or medical condition which:

1. is fatal or life-threatening
2. required or prolonged hospitalization
3. results in persistent or significant disability/incapacity
4. constitutes a congenital anomaly or a birth defect
5. is medically significant, may jeopardize the subject and may require medical or surgical intervention to prevent one of the outcomes listed above.

Events not considered to be serious adverse events are hospitalizations for the:

- routine treatment or monitoring of the studied indication, not associated with any deterioration in condition.
- treatment, which was elective or pre-planned, for a pre-existing condition that did not worsen
- treatment on an emergency, outpatient basis for an event not fulfilling any of the definitions of serious given above and not resulting in hospital admission.

Protocol Version 3: October 6, 2015

Pregnancy, although not itself an SAE, should also be reported on an SAE form or pregnancy form and be followed up to determine outcome, including spontaneous/voluntary termination, details of birth, and the presence or absence of any birth defects or congenital abnormalities.

Any SAE occurring after the patient has provided informed consent, has started taking the study medication, and until 4 weeks after the patient has stopped study participation must be reported. This includes the period in which the study protocol interferes with the standard medical treatment given to a patient (e.g. treatment withdrawal during washout period, change in treatment to a fixed dose of concomitant medication). The period after discontinuing study drug may be extended if there is a strong suspicion that the drug has not yet been eliminated.

This is a DSMP Level II study under the SKCCC Data Safety Monitoring Plan (12/6/2012). Data Monitoring of this protocol will occur on a regular basis with the frequency dependent on the rate of subject accrual and the progress of the study. The protocol will be monitored internally at SKCCC by the Principal Investigator and externally by the SKCCC CRO in accordance with SKCCC guidelines. Trial monitoring and reporting will be done through the Safety Monitoring Committee (SMC) at SKCCC.

## **7.2 Instructions for rapid notification of serious adverse events**

### **7.2.1 Reporting responsibility**

The principal investigator has the obligation to report all serious adverse events to the FDA, IRB, and Novartis Pharmaceuticals Drug Safety and Epidemiology Department (DS&E)

### **7.2.2 Reporting procedures**

All SAEs are reported to the FDA by the trial's IND Sponsor-Investigator ([name]) via the IND annual report per 21 CFR 312.33. All SAEs deemed unexpected and related to the investigational product qualify for expedited reporting and must be submitted to the FDA by the IND Sponsor-Investigator per 21 CFR 312.32 as shown immediately below. The IND Sponsor-Investigator is required to notify the FDA of any fatal or life-threatening adverse event that is unexpected and assessed by the Sponsor-Investigator to be possibly related to the use of LDE225 within 7 calendar-days of first learning of the event. An unexpected adverse event deemed possibly related to the use of an investigational study drug is defined as any adverse drug experience of which the specificity or severity is not consistent with the current investigator brochure, the general investigational plan, or elsewhere in the current application, as amended. Such reports are to be telephoned or faxed to the FDA within 7 calendar-days of first learning of the event. The IND Sponsor-Investigator is required to notify the FDA in a written IND Safety Report, of any serious, unexpected adverse event considered by the Sponsor-Investigator to be possibly related to the use of LDE225 within 15 calendar-days of first learning of the event.

In addition to the above, the investigator must complete the FDA MedWatch 3500a form and Novartis SAE coversheet in English, assess the relationship to study treatment and send the initial completed MedWatch form and Novartis SAE coversheet by [contact] within 24 hours to the local Novartis Drug Safety & Epidemiology (DS&E) Department. The investigator must then ensure that the form and coversheet are accurately and fully completed with follow-up information and fax those to Novartis DS&E Department within 2 to 3 calendar days for deaths or life-threatening events and 5 calendar days for other serious adverse events. The original and the duplicate copies of the FDA MedWatch form, Novartis

SAE coversheet, and the fax confirmation sheet must be kept with the case report forms at the study site.

Follow-up information should describe whether the event has resolved or continues, if and how it was treated, whether the blind was broken or not, and whether the patient continued or discontinued study participation. The MedWatch form, Novartis SAE coversheet, and fax confirmation sheet must be retained. Pregnancy follow-up should describe the outcome of the pregnancy, including any voluntary or spontaneous termination, details of the birth, and the presence or absence of any congenital abnormalities or birth defects.

### **7.3      Pregnancies**

Each pregnancy occurring for a female partner of a male study participant must be reported while the patient is on study treatment and for up to 6 months after the patient's last dose. Pregnancy outcomes must be collected for the female partners of any males who took study treatment in this study.

## **8           Statistical Methods and Data Analysis**

In general terms, we wish to determine if there is a statistically significant reduction in *Gli1* expression in prostate tissue after a 4-week exposure to LDE225. We expect to see significant down-regulation of *Gli1* in the treatment arm compared to the observational arm.

### **8.1      Sample size considerations, and analysis of the primary endpoint**

The primary endpoint is a  $\geq 50\%$  reduction in *Gli1* mRNA (or protein) expression following treatment with LDE225. This study will compare prostatectomy *Gli1* expression levels to presurgical biopsy *Gli1* expression levels in the same patients (*i.e.* intra-patient changes). In the control group (observation), we expect  $<10\%$  of patients to show a  $\geq 50\%$  *Gli1* downregulation (null hypothesis), while in the LDE225 group we would hypothesize that  $>50\%$  of patients would demonstrate a  $\geq 70\%$  *Gli1* downregulation (alternative hypothesis). Using a 2-sided alpha ( $\alpha$ ) of 0.10 and a beta ( $\beta$ ) of 0.20 (power = 80%), a sample size of **11 men/arm** (total = **22men**) would be required to observe a difference in the primary endpoint from  $<10\%$  (in the control arm) to  $\geq 70\%$  (in the LDE225 arm).

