### Exploratory Objectives

- (1) To evaluate genome-wide mRNA expression changes in prostate cancer induced by LDE225 exposure.

The objectives and related endpoints are summarized in the [Table](#) below.

	Objective	Endpoint	Analysis
Primary	Pharmacodynamic effect of LDE225 on prostate tissue	50% reduction in Gli1 mRNA expression comparing pre-operative prostate biopsies to radical prostatectomy specimens	qRT-PCR performed on pre-operative tumor biopsy specimens and tumor from RP specimens. Comparison performed within and between treated and untreated groups. Correlation of Gli1 levels to pre-operative Gli1 expression.
Secondary	
 
-Pathological effect on localized high-risk cancer
 
-To determine whether pre-surgical treatment with LDE225 diminishes the risk of PSA recurrence following prostatectomy
 
-To evaluate drug-related toxicities including peri-operative complications
 
	
 
-Assessment of tumor stage and grade (predicted versus actual) and changes in proliferation and apoptosis
 
-PSA <math>\geq 0.2</math> ng/ml at 3 months following prostatectomy
 
-Length of surgery, intraoperative blood loss, length of hospital stay, rates of post-operative complications (infection, wound breakdown, deep vein thrombosis, within 90 days from surgery)
 
	
 
-Routine pathologic analysis. Additionally, semi-quantitative IHC for Ki-67 and cleaved caspase-3. Comparison performed within and between treated and untreated groups.
 
-Routine serum ELISA for PSA
 
-Comparison of routinely collected intraoperative and post-operative data between treated and untreated groups
 

Exploratory	Evaluate genome-wide mRNA expression changes in prostate cancer induced by LDE225 exposure	Gene expression analysis on biopsy and prostatectomy tissue using the Affymetrix GeneChip Human Exon 1.0ST Array	Differential gene expression analysis and analysis of functional annotation comparing biopsy and prostatectomy specimens both between and within groups

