After obtaining baseline laboratory and clinical values (including an ECG, PSA, hematologic, and renal and hepatic panels), men will receive oral LDE225 800 mg/day or observation daily for 4 weeks ( $\pm 3$  days) prior to prostatectomy. Patients will have a clinical visit and an ECG and laboratory testing will be performed at 2 weeks and then again at 4 weeks, including a 4-week pre-prostatectomy measurement of PSA and a blood sample to determine plasma LDE225 levels by LC-MS/MS. Previous studies using other oral Hedgehog inhibitors indicate that 4 weeks will allow time for steady-state levels of drug in the plasma and for inhibition of *Gli1* expression ([LoRusso et al. 2011](#)).

Men will undergo radical prostatectomy (with bilateral pelvic lymphadenectomy as appropriate), at which point two 250-mg biopsies of prostate tissue will be obtained, frozen and stored for analysis (including *Gli1* expression, genome-wide expression analysis, intra-prostatic LDE225 levels, Ki-67, and cleaved caspase-3) with the remainder of the prostate tissue then being formalin-fixed paraffin-embedded (FFPE) and cross-sectioned for analysis as per our standard institutional procedures.

Relative fold-changes in mRNA expression of *Gli1* will be determined by first normalizing input amounts of the preoperative biopsy and prostatectomy biopsies to the housekeeping gene *HPRT1*. IHC comparisons between diagnostic biopsy specimens and prostatectomy specimens will be made by calculating immunoreactivity scores (staining intensity  $\times$  percentage cell involvement).

Protocol Version 3: October 6, 2015

All men will receive routine post-operative care, and in addition will have ultrasensitive PSA testing at 1 and 2 months post-op followed by standard PSA testing at the 3 month visit.

Study Schema

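### The primary Gli1 test is not fixed: section 8.1 sizes a yes/no 50% fall at alpha 0.10, section 6.2.4 compares changes at 0.05, and neither adjusts for biopsy Gli1

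*Combined protocol and SAP*

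**What the plan says.** **Endpoint.** The table in section 2 gives the primary endpoint as a 50% "reduction in Gli1 mRNA expression comparing pre-operative prostate biopsies to radical prostatectomy specimens". Section 8.1 repeats it as a fall of at least 50%, judged against "presurgical biopsy *Gli1* expression levels in the same patients".

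**Sample size.** Section 8.1 works from responder proportions. "In the control group (observation), we expect" fewer than 10% of men to reach the cut; the LDE225 figure used for the calculation is at least 70%. It continues "Using a 2-sided alpha" of 0.10 and a beta "of 0.20 (power = 80%), a sample size of 11 men/arm (total = 22men"), which "would be required to observe a difference in the primary endpoint from" the control rate to the LDE225 rate. No test is named for the primary comparison. Section 8.2 names Mantel-Haenszel for two binary secondary endpoints.

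**Continuous measurement.** Section 3.1 has each man's biopsy and prostatectomy values normalised to HPRT1 to give "Relative fold-changes in mRNA expression of" Gli1, and treats the qRT-PCR change as the main readout. Section 6.2.1 describes the primary measure as the change in Gli1 expression, with no cut. Section 6.2.4 says comparisons of normalised changes within patients and "between each group (observation versus treatment arm) will be made with 2-sided pairwise comparisons considering" P<0.05 significant.

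**Baseline.** The section 2 table lists a correlation with pre-operative Gli1. No section puts biopsy Gli1 into a model as a covariate.

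**The concern.** Two different analyses can each be read as the primary one: a comparison of responder proportions at 0.10 and a comparison of changes at 0.05. Nothing says which decides the trial. If they disagree, the choice would be made after the data are seen.

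The version that was sized also uses less of the measurement. A 50% fall is one unit on the log2 scale. With the cut, a 51% fall and a 97% fall count the same, and a 49% fall counts as nothing. The change comparison in section 6.2.4 keeps the size of the fall, but states no log scale and carries the full noise of the biopsy value.

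Section 3.2 says the trial is meant to help decide whether larger studies follow. With 22 men, an avoidable loss of power could turn a real pharmacodynamic effect into a negative result.

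**Working it through.** **Inputs from section 8.1.** 11 per arm, two-sided alpha 0.10, 80% power, responder rates 10% (control) and 70% (LDE225).

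**1. Reproduce the plan's figure.** The pooled two-proportion formula, with mean rate 0.40, gives

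n = [1.645·√(2·0.40·0.60) + 0.842·√(0.10·0.90 + 0.70·0.30)]² / 0.60² = (1.140 + 0.461)² / 0.36 = 7.12, so 8.

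The continuity correction gives (7.12/4)·[1 + √(1 + 4/(7.12·0.60))]² = 10.2, so **11 per arm**, as stated. At a 50% LDE225 rate the same corrected formula needs 20.

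**2. Responder test, exact power at 11 v 11.** All outcome pairs are enumerated and the binomial probabilities of significant pairs summed. Fisher's test and the uncorrected chi-square are shown because the plan names neither. Single-stratum Mantel-Haenszel gives the same power as chi-square here.

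**3. Continuous test.** Assume log2 change is normal with equal SD in both arms. Rates of 10% and p then imply a mean difference of z(0.90) + z(p) in SD units:

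- p = 0.70: 1.282 + 0.524 = 1.81 SD
- p = 0.50: 1.282 + 0 = 1.28 SD

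Power is from the noncentral t with 20 df and noncentrality d·√(11/2): 1.81·2.345 = 4.24 and 1.28·2.345 = 3.01.

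| Rates | Alpha | Fisher | Chi-square / M-H | t-test, log2 change |
|---|---|---|---|---|
| 10% v 70% | 0.10 | 88% | 95% | 99% |
| 10% v 70% | 0.05 | 76% | 88% | 98% |
| 10% v 50% | 0.10 | 54% | 71% | 90% |
| 10% v 50% | 0.05 | 36% | 54% | 82% |

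At alpha 0.10 the gain is 4 to 11 points in the planning case and 19 to 36 points at 50%. For 80% power at alpha 0.10, Fisher needs 10 per arm and the t-test 5 at 70%; at 50% they need 19 and 9.

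The 50% figure is a sensitivity value. Section 8.1 does mention more than 50% of LDE225 men, but for a fall of at least 70%, which is a deeper cut.

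**4. Baseline adjustment.** If r is the correlation of log2 change with log2 biopsy Gli1, ANCOVA replaces d by d/√(1−r²), with 19 df. The documents give no r. For assumed r of 0.3, 0.5 and 0.7, power at alpha 0.10 is 92%, 96% and 99% at 10% v 50%, against 90% unadjusted. At 10% v 70% it is above 99% throughout. If biopsy and prostatectomy SDs are equal, the pre-post correlation is 1 − 2r², so these r values correspond to 0.82, 0.50 and 0.02. Most of the gain comes from not dichotomising.

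**5. Sensitivity to spread.** The only Gli1 spread in the documents is from skin. In Table 1-5, the 800 mg QD row has n = 20, mean fold change 3.8 (log2 = 1.93) and interval 2.2 to 6.6. Read as a log-scale t interval, the half-width is (log2 6.6 − log2 2.2)/2 = 0.792, so SD = 0.792·√20/2.093 = 1.69.

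- *SD 1.69 in both arms, control mean 0:* Fisher 56%, chi-square 73%, t-test 82%. But Φ(−1/1.69) = 28% of untreated men would then be responders, against fewer than 10% planned.
- *SD 1.69 in treated men only, control SD 0.78* (1/1.282, which keeps control at 10%): Fisher 89%, chi-square 96%, t-test about 95%.

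**The case against.** The strongest reply is that a continuous comparison is already planned in section 6.2.4, that sections 3.1 and 6.2.1 treat the change itself as the primary measure, and that the responder test already exceeds its 80% target at the planning rates. All of that stands. It limits the size of the point, but not the need to say which analysis is primary and at what alpha.

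A second reply is that the 50% cut is the protocol's own threshold for a drug effect. A significant mean ratio could reflect a smaller average fall, say 30%. That also stands, and is why the responder rate should be kept.

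Two stronger readings are tempting. A reader might infer that the plan ignores baseline Gli1. It does not: the biopsy value is each man's reference, and a correlation with it is listed. Only covariate adjustment is missing. A reader might also infer, from 56% against 82% in step 5, that the trial throws away most of its power. That contrast puts a skin SD from treated phase I patients into the untreated arm, contradicting the planned control rate, and relies on Fisher's test, which section 8.1 does not name. With control held at 10%, the advantage is about 6 points over Fisher and none over chi-square.

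One caution applies to chi-square: at 11 per arm its type I error at nominal 10% is 5.8% for a common rate of 10%, but 11% at a rate of 30% and 13% at 50%.

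**Conclusion.** The point holds in a limited form. The primary Gli1 comparison is unfixed between a responder test at 0.10 and a comparison of changes at 0.05, and no baseline-adjusted model is planned.

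Under normal log2 changes with equal SD, analysing the change on the log2 scale at alpha 0.10 raises power from 88–95% to 99% at 10% v 70%, and from 54–71% to 90% at 10% v 50%. Baseline adjustment adds 2 to 10 points in the second case for the assumed correlations. The documents support no claim of a large loss at the planning rates. If treated men are much more variable than controls, the gain over chi-square can disappear.

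The gain is therefore real but conditional on an SD and a correlation that the documents do not give. Sections 3.1 and 3.2 themselves describe the natural fluctuation of the pathway as unknown or largely unknown, which is a reason not to rely on the favourable case.

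**What to change.** In sections 8.1 and 6.2.4, name one primary between-arm test at the section 8.1 alpha (two-sided 0.10): ANCOVA of log2 HPRT1-normalised prostatectomy Gli1 on arm, with log2 biopsy Gli1 as covariate. Report the adjusted geometric mean ratio with its confidence interval, and a rank-based ANCOVA as sensitivity check. Label the remaining Gli1 comparisons in section 6.2.4 as supporting.

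Keep the responder rate at the 50% cut in each arm, with exact confidence intervals, as a key supporting result, and align the section 2 table.

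The cost is wording, plus a restated justification for 11 per arm that gives its assumed SD of log2 change. Assays, samples and patient numbers do not change. There are two drawbacks. The test assumes roughly normal residuals on the log2 scale. A significant mean ratio does not by itself show a 50% fall, so it must be read with the responder rate.
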